
c) Background and Preliminary Results

Asymptomatic Hypotension, OH & Related Outcomes:

As early as 1927 individuals with low BP were described as those who lacked stamina, tired easily, complained of cold extremities and showed an inability to do prolonged mental or physical work. [27] However, nearly a century later, the notion that hypotension may be a clinical concern has yet to gain substantial traction. In fact, several articles have challenged the notion that low BP is a health concern, suggesting that hypotension is the ideal “normal” BP and a benefit to longevity and cardiovascular health. [28, 29] We understand that the diagnosis and treatment of disease is usually based on causal associations between symptoms and physiological pathology; [30] but the “non-disease state” has been described as the diagnosis of a particular disease when confirmatory ‘symptomology’ is not readily apparent, [31] as in the

case of low BP. [30] It must be appreciated however, that the diagnosis and treatment of high BP and hypertension are readily made, regardless of symptomology, and we noted that although only 15% of veterans with tetraplegia had clinical values entered into the medical record reflecting hypertension, 39% were diagnosed with hypertension and 54% were prescribed at least 1 anti-hypertensive medication. [6] In contrast, the diagnosis and treatment of hypotension and OH are almost exclusively made based on the presence of significant symptomology, including: orthostatic dizziness, light-headedness, pre-syncope and syncope, as well as non-specific symptoms of generalized weakness, fatigue, nausea, cognitive slowing, blurry vision, leg buckling or headache. Whereas 39% of veterans with tetraplegia had clinical values entered into the medical record reflecting hypotension, less than 1% were diagnosed or treated for the condition. [6]

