Study 1– To determine the proportion of subjects with SCI with: 1.1) a normotensive response to droxidopa and 1.2) a sustained hypertensive response to droxidopa. The dose optimization study will be scheduled to begin after completion of the screening visit. Eligible participants will be administered oral droxidopa in a dose escalation, open-label manner beginning with 200 mg. The dose will be adjusted upwards by 100 mg on subsequent visits until (1) average SBP recorded 60-120 minutes after dose administration is 111-139 mmHg in males and 101-139 mmHg in females (i.e., normotensive), (2) sustained elevation (\geq 30 consecutive minutes) in seated SBP \geq 140/100 mmHg, (3) maximum dose of 800 mg is reached without adequate SBP response or (4) intolerable side effects considered related to study medication. Subjects will visit the testing laboratory on as few as 1 (200 mg) and as many as 8 (800 mg) days, and will be asked to refrain from taking prescription anti-hypotensive agents for 12 hours prior to study. Participants with an excessive response to the 200mg dose, i.e., average 4-hour SBP above 139, will be asked to visit the laboratory to determine their blood pressure response to a 100mg dose. Based on our previous data, we do not anticipate an excessive response to the 200mg dose in most participants, we request the addition of the 100mg dose be administered only in participants with excessive responses to the 200mg dose. Subsequent study visits will be scheduled no less than 2 and no more than 10 days apart. Subjects will arrive at the laboratory between 10AM and 1PM after a light breakfast and having avoided alcohol, caffeine, and nicotine for 12-hours. Subjects will remain in their wheelchair for instrumentation, which will include: 1) 3-lead electrocardiogram (ECG) for continuous recording of heart rate (HR) and respiration rate; 2) brachial BP, which will be monitored using a manual sphygmomanometer and finger arteriolar beat-to-beat BP, which will be recorded using photoplethysmography with a cuff placed around the middle or index finger of the left hand. Seated cardiovascular hemodynamic assessments will be monitored and recorded at 15-minute intervals for 4-hours, and the side effects questionnaire (Appendix 4) will be administered hourly during the 4-hour study. Individuals who do not respond to droxidopa with a normal seated SBP will be excluded from Study 2. Each study visit will take about 5 hours.

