administration and subjects will remain in the 70° HUT position for 30 minutes or until symptoms of syncope develop. Orthostatic HR, finger BP and CBFv will be monitored continuously for 5-minutes at 0, 10 and 20 minutes during the HUT and brachial BP will be monitored and recorded at 0, 5, 10, 15, 20, 25 and 30 minutes. Additionally, subjects will be asked questions related to the symptoms of OH at 10 minute intervals during the sustained HUT maneuver (Appendix 5). After completion of the HUT maneuver subjects will be transferred to their wheelchair for continued monitoring of seated SBP (until within $\pm 10\%$ of baseline SBP) and will be asked questions pertaining to the side-effects of droxidopa (Appendix 4). Because hypotensive individuals with SCI self-report an increased incidence of fatigue, we will assess fatigue using the Visual Analog Fatigue Scale (VAFS) during the two visits to determine if BP elevation, with droxidopa, reduces fatigue symptoms compared to placebo (Appendix 6). These visits will take about 5 hours.

Cardiovascular Assessments:

- **Electrocardiogram** - A 3-lead ECG (UFI: model RESP 1, Morro Bay CA) will be used to measure beat-to-beat HR and respiration rate (RR) during testing. Electrodes will be placed at the right and left clavicle and in the V-5 position; data will be recorded from V-5. HR and RR signals will be viewed in real time and will be stored for analysis of cardiovascular autonomic control (via heart rate variability techniques: HRV) using customized programs written with LabView graphical software.
- **Finger Arteriolar Blood Pressure** Beat-to-beat BP will be continuously monitored from the left middle or ring finger using photoplethysmography (FMS: Finometer, Pro; Amsterdam, Netherlands). Finger arteriolar BP will be viewed in real time on a computer screen during the supine, seated and HUT observation periods and will be stored for analysis to estimate sympathetic influences on vascular control (BP variability: BPV) using customized programs written with LabView graphical software.
- **Brachial Blood Pressure** - Brachial BP will measured by a trained technician using a standard adult BP cuff (GE Healthcare Information Technologies, Milwaukee, WI) with a manual sphygmomanometer at 5-15 minute intervals during studies 1 and 2.

Cerebrovascular Assessments:

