- **Cerebral Blood Flow Velocity** – will be monitored using Transcranial Doppler (TCD) ultrasound (Terumo Cardiovascular Systems [name]) to assess blood flow velocity (cm/s) at the left middle cerebral artery (MCA) through the temporal window. The MCA signature will be identified by the depth (45-55 mm), sound and direction of flow (towards the probe), as evidenced by the color and spectral waveform. The TCD probe will be operated at a frequency of 2.0 MHz to visualize the MCA through the temporal window; once visualized, a head-harness will be used to secure probe placement for the duration of testing. TCD recordings of CBFv will be viewed in real-time continuously throughout testing and will be recorded at intervals described above. The raw analog CBFv signal will be digitized and stored for subsequent analysis using customized programs created with LabView graphical software.

Blood Draws:

- Four plasma samples (20 mL per sample) will be drawn from an antecubital vein for analysis of changes in plasma renin, serum aldosterone and plasma norepinephrine concentrations following administration of droxidopa compared to placebo. Concentration of these vasoactive substances are altered during orthostatic provocation, which may be differentially affected by study drug compared to placebo.

Surveys

- **Vancouver Coastal Health Autonomic Dysfunction following SCI Survey** (Appendix 3) - will be used to determine the frequency and severity of the common symptoms and side effects of AD and OH.
- **Side-Effects Survey** (Appendix 4) – The most common side-effects reported with droxidopa are headache (%) dizziness (%) nausea (%) hypertension (%) and fatigue. In addition, subjects may report: feeling feverish, muscle cramps, confusion and uncontrolled movements. Therefore, we will ask participants questions related to these known side-effects and will gather data on any other subject symptom that may be related to the study medication.
- **The Visual Analog Fatigue Scale** (Appendix 5) – will be used one time per study visit to determine the effects of droxidopa dose (Study 1) compared to placebo (Study 2) on self-report severity of fatigue.

Data Analysis:

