This is a pilot trial to determine the dose efficacy and safety of droxidopa to increase systemic BP and improve orthostatic BP and CBFv responses compared to placebo in hypotensive individuals with SCI. Because this is a pilot trial, the following statistical analyses are not powered for a specific effect size; however, the results will be used to power a subsequent large scale clinical trial to identify the utility and safety of droxidopa for treatment of asymptomatic hypotension in persons with SCI.

Primary Aim 1.1: Dose optimization, open-label trial to determine the proportion of subjects with SCI with a normotensive response to droxidopa (**Efficacy #1**). Normotension will be defined as an average systolic BP (SBP) recorded 60-120 minutes after dose administration of between 111-139 mmHg in males and 101-139 mmHg in females.

- **Hypothesis 1.1** – Seated SBP will be normalized in 60% of the study sample following administration of droxidopa.
 - This hypothesis will be tested by constructing a 95% confidence interval about the sample proportion of cases in which BP is normalized with droxidopa. The inclusion of the 60% value in the confidence interval will be taken as evidence in support of the hypothesis. Further, the point estimate and confidence interval will provide the first reported estimate of the BP normalizing effect of droxidopa in the population with SCI.

Primary Aim 1.2: Dose optimization, open-label trial to determine the proportion of subjects with SCI with a hypertensive response to droxidopa (**Safety #1**). Hypertension will be defined as a sustained elevation in seated SBP \geq 140/100 mmHg or intolerable side effects considered related to study medication

- **Hypothesis 1.2** – Less than 10% of the study sample will exhibit hypertension or intolerable side effects related to administration of droxidopa.

- This hypothesis will be tested by constructing a 95% confidence interval about the proportion of cases in which either seated BP $\geq 140/100$ or intolerable side effects occur. If the 95% CI excludes values $\geq 10\%$, this will be taken as evidence in support of the hypothesis. Further, the point estimate and confidence interval will provide the first reported estimate of the expected side effects of droxidopa treatment in the population with SCI.

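### Hypothesis 1.2 offers an uncontrolled, open-label rate as the estimate of droxidopa's expected side effects, while the same survey taken on blinded droxidopa and placebo days in Study 2 has no specified analysis

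*Protocol*

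**What the plan says.** **Source of the estimate.** Study 1 is uncontrolled: "Eligible participants will be administered oral droxidopa in a dose escalation, open-label manner beginning with 200 mg" (Protocol, Research Design and Methods, Study 1). Hypothesis 1.2 (Protocol, Data Analysis; repeated in the Combined protocol and SAP, item 17a) reads: "Less than 10% of the study sample will exhibit hypertension or intolerable side effects related to administration of droxidopa". The result is then described as the "first reported estimate of the expected side effects of droxidopa treatment in the population with SCI".

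**Relatedness.** The endpoint definition counts "intolerable side effects considered related to study medication". The analysis bullet, which plans "constructing a 95% confidence interval about the proportion of cases in which either seated BP" reaches the threshold or intolerable side effects occur, has no relatedness condition. Neither document names who judges relatedness.

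**Overlap with the condition.** The Side-Effects Survey paragraph (Protocol, Surveys) states: "The most common side-effects reported with droxidopa are headache (%) dizziness (%) nausea (%) hypertension (%) and fatigue". The Background section lists orthostatic dizziness among the symptoms of hypotension and orthostatic hypotension, together with "non-specific symptoms of generalized weakness, fatigue, nausea, cognitive slowing, blurry vision, leg buckling or headache". It also names headache as a symptom of autonomic dysreflexia.

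**Collection in Study 2.** The Appendix 4 survey is given hourly over 4 hours in Study 1, and again after the head-up tilt at both Study 2 visits. Study 2 is a double-blind crossover in which each participant takes droxidopa and placebo. Hypotheses 2.1A to 2.4 cover supine blood pressure, tilt blood pressure, cerebral blood flow velocity and hormones. None uses Appendix 4, and no descriptive table of it is specified.

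**The concern.** An uncontrolled rate is what happened to people while they were taking the drug. To call it the expected side effects of the drug needs either a comparator or a reliable causal judgement, and Study 1 has neither. Everyone knows the drug and dose, and headache, dizziness, nausea and fatigue can come from the condition. Fatigue shows the difficulty best: the Surveys section lists it as a side effect, while the Study 2 section asks whether droxidopa reduces it compared with placebo.

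The error can run either way. A symptom of the condition can be blamed on the drug, or a drug effect put down to the condition. The two statements of the endpoint, with and without relatedness, can also give different answers from the same data. The trial is meant to inform a larger study of utility and safety, so the side-effect figure is likely to be carried forward.

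**Working it through.** The documents give no event rate, power or precision for this endpoint, so there is no planned figure to reproduce. Three checks show the size of the problem.

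**1. How many events decide Hypothesis 1.2.** Inputs: about 40 participants in Study 1 (Protocol, Study Population) or 60 (Combined document, item 4); 95% interval, method not named, two-sided assumed; criterion that the interval excludes values of 10% or more. Exact (Clopper-Pearson) upper limits:

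| n | Events | Upper limit | Criterion met |
|---|---|---|---|
| 40 | 0 | 8.8% | yes |
| 40 | 1 | 13.2% | no |
| 60 | 1 | 8.9% | yes |
| 60 | 2 | 11.5% | no |

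For 0 of 40 the formula is 1 − 0.025^(1/40) = 0.088. Wilson intervals give the same cut-offs; Wald intervals allow 1 event (n = 40) and 2 events (n = 60). Suppose the only event among 40 is an intolerable headache judged unrelated. The definition counts 0 events and the hypothesis is supported; the analysis bullet counts 1 and it is not.

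**2. What background symptoms could do.** Suppose an intolerable symptom not caused by the drug has probability b per visit and is attributed to the drug. Over k visits a participant has one or more with probability 1 − (1 − b)^k. Steps of 100 mg from 200 to 800 mg give up to (800 − 200)/100 + 1 = 7 doses. With b = 1% (assumed):

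- k = 7: 1 − 0.99^7 = 6.8%. With no true drug effect, the chance of meeting the criterion is 6% (n = 40) or 8% (n = 60).
- k = 4: 1 − 0.99^4 = 3.9%. The chance is 20% (n = 40) or 31% (n = 60).

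With b = 2% and k = 7 the cumulative rate is 13.2%, above the threshold with no drug effect at all. The documents give no value for b. This shows sensitivity, not a predicted bias, and it ignores attribution errors in the other direction.

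**3. What Study 2 could add.** Inputs: 25 participants (Protocol) or 30 (Combined document). For a paired difference near zero, the approximate 95% half-width is 1.96 × √(discordant proportion / n). The discordant proportions are assumed:

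| n | 20% discordant | 30% discordant |
|---|---|---|
| 25 | 17.5 points | 21.5 points |
| 30 | 16.0 points | 19.6 points |

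For a non-zero difference d between the droxidopa-only and placebo-only proportions p₁ and p₂, the standard error is √[(p₁ + p₂ − d²)/n]:

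| Droxidopa-only / placebo-only (assumed) | d | 95% CI, n = 25 | 95% CI, n = 30 | Exact McNemar power, n = 25 / 30 |
|---|---|---|---|---|
| 20% / 5% | 15 points | −3.7 to 33.7 | −2.1 to 32.1 | 17% / 24% |
| 30% / 10% | 20 points | −3.5 to 43.5 | −1.5 to 41.5 | 24% / 31% |
| 40% / 10% | 30 points | 4.9 to 55.1 | 7.1 to 52.9 | 48% / 59% |

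The comparison is feasible as an estimate with an interval, but not as a powered test.

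**The case against.** **This is an unpowered pilot, and an uncontrolled incidence is a normal product of open-label dose finding.** True, and the sentence on expected side effects could be read as descriptive. That supports keeping the Study 1 rate. It also supports labelling it for what it is.

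**A reader might infer that the side-effect statement should be moved to Study 2, as the only unbiased contrast.** The documents do not support this. Hypothesis 1.2 concerns intolerable effects, which are a reason to stop escalation in Study 1. Study 2 admits only people with a normal seated pressure response, at one individualized dose, so those who stopped for intolerable effects without such a response never enter it. Its survey also follows up to 30 minutes at 70 degrees, or a tilt ended by symptoms of syncope. If droxidopa supports pressure during tilt, as Hypothesis 2.2 expects, the placebo day could produce more dizziness or nausea, and the drug could look protective. Study 2 offers the only blinded, placebo-controlled contrast of these symptoms, which is a narrower claim.

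**A reader might also infer that investigators are shown to decide which events count.** No assessor is named. Only the lack of blinding follows, from the open-label design.

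**The overlap of four in five is not a measure of bias.** This stands. Most of this population is described as asymptomatic, Study 1 is seated, and the word intolerable filters out mild symptoms. No background rate is given, so size and direction are unknown.

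**Study 2 safety is not ignored.** Supine hypertension is compared with placebo in Hypothesis 2.1B. Comparing fatigue with placebo is a stated purpose, though without a specified test. An independent monitor reviews symptom trends in aggregate (Protocol, Safety Monitoring), but that is oversight and not a planned treatment comparison of the survey.

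**Conclusion.** The point holds as a matter of labelling and of one missing table. Study 1 can give an uncontrolled incidence of a composite during open-label escalation; it cannot by itself give the expected side effects of the drug. The inconsistency over relatedness matters because the criterion turns on 0 versus 1 event at n = 40, or 1 versus 2 at n = 60 (exact or Wilson interval). The sustained seated hypertension component is measured, so the attribution concern applies only to the side-effect component.

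Study 2 can supplement this estimate but not replace it. Its half-width of about 16 to 22 points rests on an assumed 20 to 30% of discordant pairs and a difference near zero. Intolerable events would probably give fewer discordant pairs, and the simple normal-approximation interval would then be unreliable at this sample size. The amount of misattribution in Study 1 cannot be estimated from the documents.

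**What to change.** - **Study 2.** Add one table giving, for each Appendix 4 item and for any side effect, the paired droxidopa-minus-placebo difference in the proportion of participants reporting it. Use a 95% interval for paired proportions suited to small samples, such as a Newcombe or Tango score interval. Call it a descriptive supplement without hypothesis tests, since the Surveys section already names nine effects. State with it that it covers only Study 1 responders at one individualized dose, that the survey follows the tilt so the difference mixes orthostatic benefit with adverse effects, and that precision is low.
- **Study 1.** Keep it as the source for intolerable effects. Report them both regardless of attribution and as judged related, state which count enters the Hypothesis 1.2 criterion, and label both uncontrolled.
- **Wording.** In both documents, replace the description of the Hypothesis 1.2 result with *uncontrolled incidence during open-label dose escalation*.

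Cost: a few sentences of analysis-plan text and one table. No new visits or data are needed, and Hypothesis 2.1B already plans differences between dependent proportions. The price is wide intervals and a claim restricted to responders.

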significantly increased in those who responded to the 400 mg dose of droxidopa compared to the non-responders (105 ± 10 vs. 81 ± 10 mmHg, respectively; $p=0.0048$), and although the magnitude of effect was doubled in the non-responders, the SBP response did not differ significantly (9.0 ± 10 vs. 18.6 ± 16 mmHg, respectively; $p=0.2937$). These data suggest that individuals with a seated SBP below 95 mmHg may need a higher dose of droxidopa to normalize SBP.

d) Research Design and Methods

We propose to determine the dose of droxidopa that normalizes seated SBP in hypotensive individuals with SCI, and to determine the effect of that dose of droxidopa on supine BP, orthostatic BP and CBFv compared to placebo.

Study Population: Fifty subjects with SCI will be screened for study eligibility. We anticipate that approximately 40 of the subjects screened will be eligible and will undergo the dose optimization trial (**Study 1**). We anticipate that 25 subjects will respond to droxidopa with a normal seated SBP, and these individuals will be eligible for the randomized placebo-controlled trial to determine the effect of the optimal dose on supine BP, orthostatic BP and CBFv compared to placebo (**Study 2**). Each subject will be randomized by the Research Pharmacy to receive either droxidopa/placebo or placebo/droxidopa for the placebo-controlled prospective trial. Randomization will occur in a double-blinded manner. Study medication and placebo will be distributed by the James J Peters VAMC Pharmacy Service. The study is proposed to be completed in two years. Total enrollment will be accomplished within 18 months of obtaining full IRB approval, which should be complete within 6 months of funding, and subject participation is estimated to last about 6-8 weeks. A complete description of the study population can be found in the Human Subjects Form 11.

Study Procedures: Identical testing procedures will be performed at the JJP VAMC and the ISMMS according to the table below.

Procedures Table	Screening	Study 1									Study 2	
		1	2	3	4	5	6	7	8	9	10	11
Visit												
Medical Intake	X											
Medical History	X											
OH Survey	X											
AD Survey	X											
Seated BP	X	X	X	X	X	X	X	X	X	X	X	
Supine BP	X										X	X
HUT BP											X	X
CBFv											X	X
Side-effects		X	X	X	X	X	X	X	X	X	X	X
OH Symptoms Survey											X	X
Fatigue Survey	X										X	X

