Following identification of the optimal dose subjects will undergo a washout period of no less than 2 and no more than 10 days. The minimum 2-day washout was chosen because of the known 2- to 3-hour plasma half-life of droxidopa. [17]

Study 2 – To determine the effect of droxidopa, compared to placebo, on: 2.1A) supine SBP (mmHg); 2.1B) proportion of supine BP observations \geq 140/100 mmHg; 2.2) SBP during a HUT and 2.3) change in CBFv from supine to HUT. Within about 1 week of determining the dose of droxidopa that normalizes seated SBP eligible participants will return to the laboratory for the placebo-controlled randomization trial. Subjects will arrive at the laboratory between 10AM and 1PM after a light breakfast and having avoided alcohol, caffeine, and nicotine for 12-hours. Subjects will remain in their wheelchair for instrumentation, which will include: 1) ECG, 2) brachial BP, 3) finger arteriolar BP and 4) CBFv. After instrumentation subjects will be transferred to the supine position (on the tilt table) for a 10-minute period of quiet rest and baseline supine data collection. Participants will then be administered either oral droxidopa or matching placebo in a double-blinded manner and will remain in the supine

position for 60 minutes. Supine HR, finger BP and CBFv will be monitored continuously for 5-minutes at 0, 25 and 55 minutes, supine brachial BP will be monitored and recorded at 0, 10, 20, 30, 40, 50 and 60 minutes. The HUT maneuver will be initiated 60 minutes post-droxidopa/placebo

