Secondary Aims: To determine the effect of the individualized optimal dose of droxidopa, compared to placebo, on (1) supine BP (**Safety #2**), (2) SBP during a head-up tilt (HUT) maneuver to 70° (**Efficacy #2**) and change in cerebral blood flow velocity (CBFv) from supine to HUT (**Efficacy #3**). The following hypotheses will be tested in hypotensive individuals with SCI:

- **Hypothesis 2.1A** – Average supine SBP will be significantly increased following droxidopa administration compared to placebo.
 - This hypothesis will be tested using a repeated measures analysis of covariance where the pre-droxidopa or placebo SBP will be used as the covariate and the adjusted post-test scores will serve as the dependent variable. In addition, the covariate adjusted point estimate and 95% confidence interval of the difference between drug conditions will provide the first reported estimate of the supine SBP response to droxidopa versus placebo in the SCI population.
- **Hypothesis 2.1B** – The proportion of supine BP observations $\geq 140/100$ mmHg following droxidopa administration will not differ significantly from the proportion observed during the placebo trial.
 - This hypothesis will be tested by performing separate (one each for systolic and diastolic pressure) tests of the differences between dependent proportions, from which the 95% confidence intervals will be calculated. The presence of zero in a confidence interval will indicate a lack of statistical difference in incidence of hypertensive events between the droxidopa and placebo conditions.
- **Hypothesis 2.2** – Average SBP during 70° HUT will be significantly increased following droxidopa administration compared to placebo.
 - This hypothesis will be tested by performing a dependent t-test between the mean SBP during 70° HUT comparing droxidopa to placebo. Further, the point estimate and resulting 95% confidence interval will provide an estimate of the SBP response to HUT of droxidopa versus placebo in the SCI population.
- **Hypothesis 2.3** – The change in CBFv from supine to HUT will be significantly attenuated following droxidopa administration compared to placebo.

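### Hypothesis 2.1B is worded on supine readings but names a test that needs one yes/no pair per participant; if readings are pooled, the 95% CI can be up to about two-fold too narrow

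*Protocol*

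**What the plan says.** In the Protocol (Data Analysis, Secondary Aims, Hypothesis 2.1B) the outcome is "The proportion of supine BP observations" at or above 140/100 mmHg after dosing, and the hypothesis is that droxidopa and placebo do not differ. The analysis is "separate (one each for systolic and diastolic pressure) tests of the differences between dependent proportions", each with a 95% confidence interval. The decision rule is: "The presence of zero in a confidence interval will indicate a lack of statistical difference in incidence of hypertensive events" between the two conditions. Section 17a of the combined protocol and SAP repeats this text.

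The readings come from Study 2, where "supine brachial BP will be monitored and recorded at 0, 10, 20, 30, 40, 50 and 60 minutes". Study 2 is a two-period crossover: each participant is randomised "to receive either droxidopa/placebo or placebo/droxidopa for the placebo-controlled prospective trial". The Protocol (Study Population) expects 25 participants in Study 2; the combined document (sections 4a and 4b) plans 30.

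For Hypothesis 2.1B neither document states whether the unit is the reading or the participant, which dependent-proportions test is meant, or how several readings from one visit enter the interval. No per-person summary, clustered standard error or model with a participant effect is given.

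**The concern.** A test of dependent proportions assumes independent pairs, each giving one yes/no result per condition. The outcome here is a share of readings. Matching the reading at each time point on droxidopa with the reading at the same time point on placebo, and entering every match as a pair, accounts for each person being measured under both conditions. It does not account for the six or seven readings of one visit moving together. If a person's pressure runs high on one of the two days for reasons unrelated to treatment, that single event enters as several pairs in the same direction.

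Two things are at stake. The first is the decision rule, which turns only on whether zero lies in the interval: an interval that is too narrow excludes zero too often. The second is the interval itself, because both documents say that the results will be used to power a later large trial.

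**Working it through.** The documents give no power, correlation or interval width for Hypothesis 2.1B, so there is no stated figure to reproduce.

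**Inputs**
- Participants: n = 25 (Protocol) or 30 (combined document).
- Readings per visit: m = 7 (Protocol, Study 2), or 6 without minute 0.
- Pairs if pooled: 25 × 6 = 150, 25 × 7 = 175, 30 × 6 = 180, 30 × 7 = 210.
- ICC: the correlation, within a person, of the reading-by-reading differences (droxidopa minus placebo). It is not given, so a range is shown.

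**Step 1: design effect.** DEFF = 1 + (m − 1) × ICC. The correct interval is √DEFF times the pooled one. Actual coverage of the pooled interval is 2Φ(1.96/√DEFF) − 1.

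| ICC | m = 6: factor (coverage) | m = 7: factor (coverage) |
|---|---|---|
| 0 | 1.00 (95%) | 1.00 (95%) |
| 0.1 | 1.22 (89%) | 1.26 (88%) |
| 0.3 | 1.58 (79%) | 1.67 (76%) |
| 0.5 | 1.87 (71%) | 2.00 (67%) |

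For example, m = 7 and ICC = 0.5 give DEFF = 1 + 6 × 0.5 = 4. The factor is √4 = 2, and 175 pairs carry the information of 175/4 ≈ 44.

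**Step 2: what the preliminary data suggest about clustering.** The Protocol (Preliminary Data) reports the share of normotensive seated readings in 10 people as 19.3 ± 29.5% (no drug), 11.8 ± 23.3% (100 mg), 18.9 ± 21.8% (200 mg) and 42.3 ± 28.5% (400 mg). It also says that three readings made up 3% of the total, so 3/0.03 = 100 readings, about 10 each. I take ± as the SD of per-person shares (an assumption).

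ICC = [SD² / (p(1 − p)/m) − 1] / (m − 1), with m = 10:
- No drug: 0.295² / (0.193 × 0.807/10) = 5.59; (5.59 − 1)/9 = 0.51.
- 200 mg: 0.218² / (0.189 × 0.811/10) = 3.10; (3.10 − 1)/9 = 0.23.
- 100 mg and 400 mg: 0.47 and 0.26.

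These are single-condition values, and the stable-person part of them cancels in the paired difference. If nothing cancelled, the factor for six or seven readings would be about 1.5 to 2.0. If the correlation were only a stable person effect, it would be 1.0.

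**Step 3: simulated coverage.** No drug effect, n = 25, m = 7, 10% of readings high, 4,000 runs per setting:

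| ICC of differences | Pooled coverage | Participant-level paired t coverage |
|---|---|---|
| 0 (stable person effect only) | 94% | 95% |
| 0.21 | 81% | 96% |
| 0.32 | 75% | 96% |
| 0.48 | 66% | 95% |

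At ICC 0.32 the half-width is 0.058 pooled against 0.102 at participant level (0.102/0.058 ≈ 1.8).

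**Step 4: false rejection at a nominal 5%.** Assumed: 25 to 30 people, six readings, between-person SD 12 mmHg, reading SD 6 to 8 mmHg, and 2 to 20% of readings high. With no visit-to-visit variation, the pooled test rejects about 3 to 6%. With a visit-to-visit SD of 4 to 10 mmHg it rejects about 8 to 30%, least when high readings are rare. The participant-level paired t stays at or below about 5%, and falls below about 1% when only some 2% of readings are high.

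**Step 5: a conflicting schedule.** The procedures table in section 13b of the combined document lists brachial pressure once a minute at all visits. Over the 60-minute supine period m would be about 60, and an ICC of 0.1 alone would give √(1 + 59 × 0.1) = 2.63.

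**The case against.** A reader might infer that the plan assumes independent readings. It does not say so. It calls the proportions dependent and leaves the unit of pairing open. The rule "The presence of zero in a confidence interval will indicate a lack of statistical difference in incidence of hypertensive events" could describe a yes/no event per participant, to which the named test applies properly. The preliminary data are also reported both ways, as what look like per-person shares with SDs and as a pooled share of all recordings. So the defect is an unstated unit, and the narrow interval follows only if readings are pooled. Even so, the hypothesis is worded on observations whereas the primary aims are worded on subjects, and a per-person fraction is not a yes/no outcome. The text therefore needs changing on any reading except any-high-reading per participant, which it does not state.

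A reader might also infer that the interval is certain to be far too narrow. The crossover removes any stable person effect, and in that case the pooled analysis is close to correct. The documents do describe wide and frequent pressure fluctuations in this population and varied individual responses to droxidopa, so some visit-level variation is likely, but its size is not given.

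High readings may also be rare. Screening excludes sustained supine or seated elevation, and 3% of the earlier seated readings at 400 mg were at or above 140 mmHg. Rarity lowers the inflation, and it makes a participant-level paired t very conservative. That stands, and it affects the choice of fix.

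Finally, Safety #2 does not rest on this interval alone, since Hypothesis 2.1A also tests supine systolic pressure. The trial is an unpowered pilot, and the pooled point estimate is not biased by clustering. Only the stated precision is affected.

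**Conclusion.** The point holds as an unspecified unit of analysis with a conditional consequence. If readings are pooled as worded, the 95% interval is too narrow by a factor from 1.0 to about 2.0 for six or seven readings, and the documents cannot fix where in that range it falls. The upper end assumes a correlation of the within-person differences of about 0.5. That is the top of what the preliminary data suggest, and those data are seated, concern the normotensive range, come from 10 people and describe single conditions. The 8 to 30% false rejection rate rests on assumed visit-to-visit SDs of 4 to 10 mmHg and on the other SDs listed in the working.

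A reader might infer that the flaw could hide a hypertensive effect of the drug. It works the other way. Too narrow an interval excludes zero too often, against the plan's own hypothesis of no difference, so it yields false differences and not false reassurance. The amendment is worth making because it is cheap and because, as written, two competent analysts could reach opposite conclusions from the same data.

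**What to change.** Amend Hypothesis 2.1B in the Protocol and in section 17a of the combined document so that the participant is the unit. Choose one of these in advance:

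- For each participant, and separately for systolic and diastolic pressure, compute the fraction of post-dose supine readings at or above the limit on droxidopa minus that on placebo. Report the mean difference with a 95% CI from a paired method, or from a bootstrap or permutation method that resamples or permutes whole participants. The resampling form is preferable to a paired t if high readings turn out to be rare.
- Classify each visit as having any supine reading at or above the limit or none, and use an exact McNemar test with its CI.

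Also state whether the minute 0 reading counts, and reconcile the brachial reading schedule in the Protocol (Study 2) with the procedures table in section 13b of the combined document.

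The cost is wording only; no new data are needed. The downside is a wider interval wherever readings cluster, and low sensitivity when events are few. With five discordant participants, the smallest possible two-sided exact McNemar p-value is 2 × 0.5⁵ = 0.0625, so significance at 5% is out of reach. The amendment should therefore also say that zero inside the interval does not show that the conditions are the same, and that the interval is reported as an estimate with its full range.
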